3.2 Efficacy Endpoint

The efficacy endpoint for this study is the change in total score of the hyperphagia questionnaire for clinical trials (HQ-CT) from Baseline to Study Completion/Early Withdrawal, where baseline is defined as Visit 10 of INS011-16-085. The HQ-CT is a 9-item questionnaire and the response for each item ranges from 0 (for responses such as "Not at all" or "Never") to 4 (for responses such as "Several times"). The total HQ-CT score is calculated by adding the responses to each item, thereby yielding a total HQ-CT score which can range from 0 to 36 (Fehnel, et al., 2015).

4. Analysis populations

4.1 All Enrolled Population

All patients enrolled will be included in the all enrolled population.

Sponsor Name: Insys Development Company, Inc.

Sponsor Protocol ID: INS011-17-115 Covance Study ID: 000000163385

4.2 Special Subpopulations

Not applicable.

5. DATA Handling

5.1 Time points and Visit Windows

Day 1 is defined as the date of enrollment onto INS011-17-115 study. Relative days after Day 1 are calculated as (assessment date – Day 1 date) + 1. Relative days prior to Day 1 are calculated as (assessment date – Day 1 date). The day prior to Day 1 is Day -1.

All data will be analyzed using nominal study visits as defined in the Study Schedule (see Appendix A). No visit windows will be applied for summary and analysis.

Multiple visits within the same protocol-defined scheduled window (see Appendix A) will be dealt with as follows:

• If multiple scheduled visits occur within a single protocol-defined visit window then the visit closest to the target day of the visit window will be used in the analysis. In cases where the measurements are equal distances from the target day, the later visit will be used in the analysis.

5.2 Handling of Dropouts, Missing Data, and Outliers

There will be no imputation of missing data. All summaries will be based on observed data only.

For adverse events (AEs) with missing or partial start date:

- If the partial onset date does not indicate whether the AE started prior to or after the end of the treatment-emergent period (last dose of double-blind treatment plus 14 days), the AE will be classified as treatment-emergent.
- If the AE onset date is partial or missing, the AE end date will be considered. If the AE end date is partial and the partial end date does not indicate that the AE ended prior to the start of double-blind treatment, the AE will be classified as treatment-emergent.

In the event that a partial date for concomitant medication is available, this partial information will be used as follows:

 If the partial start date does not indicate whether the medication started prior to or after double-blind treatment, the medication will be classified as both prior and concomitant.

Sponsor Name: Insys Development Company, Inc.

Sponsor Protocol ID: INS011-17-115 Covance Study ID: 000000163385

 If the partial end date does not indicate that the medication ended prior to the start of double-blind treatment, the medication will be classified as both prior and concomitant.

The imputations for AEs and medications are for categorization purposes only and will not be used in listings.

6. Statistical Methods

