4.5. Blinding and Unblinding Treatment Assignment

Not applicable. This is an open-label study.

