2.2 Overall Study Design

This is a multicenter, open-label study designed to assess long-term safety and tolerability of CBD in patients with PWS. Patients must have completed INS011-16-085 to be eligible for this study.

Patients may enroll in this long-term safety study after completing INS011-16-085 Visit 10 (Study Completion) to avoid interruption of the investigational medicinal product (IMP). Patients will have up to 2 weeks to enroll in INS011-17-115. If a patient does not enroll within the 2-week window, they will not be eligible to enroll into the study.

[figure not shown]
Patients will receive CBD treatment for approximately 48 weeks. Total daily doses ranging from 20 mg/kg/day to 40 mg/kg/day will be administered with standard meal. Patients may have their dose of study medication adjusted down once from 40 mg/kg/day to 30 mg/kg/day or from 30 mg/kg/day to 20 mg/kg/day at the discretion of the Investigator or qualified designee based on the patient's tolerability. If the lower dose is not tolerated, the drug will be discontinued and the patient will be withdrawn from the study.

The study consists of a Safety Period (48 \pm 2 weeks), Taper Period (6 \pm 3 days), and a Follow-up Period (30 \pm 5 days).

The study design is presented in Figure 1.

Sponsor Name: Insys Development Company, Inc.

Sponsor Protocol ID: INS011-17-115 Covance Study ID: 000000163385

All screening, efficacy and safety evaluations will be performed according to the schedule of assessments presented in Appendix A.

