6.7.2 Adverse Events

All AEs recorded on the eCRF will be coded using the MedDRA dictionary [Version 21.1 (or a later version if updated during the study)] and classified as treatment – emergent AEs (TEAEs) as follows:

• TEAEs are events with start date on or after the date of first dose of IMP and up to 14 days after the last dose of IMP or events with start date prior to the date of first dose of IMP whose severity worsens on or after the date of first dose of IMP on INSO11-17-115.

All AE data will be listed by treatment group. Treatment-emergence status will be flagged in the listing. In addition, corresponding listings of treatment-emergent serious AEs (TESAEs), AEs leading to permanent discontinuation of IMP and AEs resulting in death will be produced. AE ongoing or worsened from INS011-16-085 will be listed.

Summary tables of TEAEs by treatment group and overall will be produced for the enrolled population. No statistical comparisons of AEs between treatment groups will be performed.

The severity of all AEs is recorded as mild, moderate, or severe. If severity is missing for a TEAE, it will be considered severe.

The relationship between an AE and IMP treatment is assessed as definite, probable, possible, unlikely or not related. A treatment-related AE is an AE considered by the investigator as definitely, possibly, or probably related to IMP treatment or with unknown/missing relationship to IMP treatment.

An overview table will summarize the number and percentage of patients with at least one of the following TEAEs, where patients with more than one TEAE in a particular category are counted only once in that category:

Sponsor Name: Insys Development Company, Inc.

Sponsor Protocol ID: INS011-17-115 Covance Study ID: 000000163385

- any TEAE;
- TEAE by severity (mild, moderate, severe);
- treatment-related TEAE;
- severe treatment-related TEAE;
- TESAE;
- TESAE by severity;
- treatment-related TESAE;
- TEAE leading to study drug discontinuation.

The overview table will be repeated to summarize the number of TEAEs (displaying the number and percentage of observed events).

The number and percentage of patients reporting each AE will be summarized by System Organ Class (SOC) and Preferred Term (PT) for all enrolled patients. Tables will be sorted alphabetically by SOC. PTs will be sorted by descending overall total. The following summaries will be produced:

- TEAEs, by SOC and PT;
- TEAEs related to IMP treatment, by SOC and PT;

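### SAP 6.7.2 treats a TEAE with missing severity as severe but leaves it out of the SOC and PT counts; secondarily, the SAP 5.2 partial-date rules rest on a double-blind treatment this open-label trial does not have

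*SAP*

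**What the plan says.** **Missing severity (SAP 6.7.2).** The section first rules that a TEAE without a severity grade is handled as severe. After the list of SOC/PT summaries comes a paragraph of counting rules. It opens by referring back to the summaries above, then explains how the maximum-severity tables count patients. It ends by saying that TEAEs lacking severity stay, as severe, in the overall patient tally but are not counted within any SOC or PT. Missing relationship is handled differently: such an event counts as treatment-related, with no exclusion.

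**Partial dates (SAP 5.2).** There are two AE rules and two medication rules.

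- AE rule 1 applies when a partial onset does not show whether the event began before or after "the end of the treatment-emergent period (last dose of double-blind treatment plus 14 days), the AE will be classified as treatment-emergent".
- AE rule 2 begins: "If the AE onset date is partial or missing, the AE end date will be considered". Its only stated outcome, treatment-emergent, is for a partial end date: "If the AE end date is partial and the partial end date does not indicate that the AE ended prior to the start" (again with double-blind treatment as the reference).
- The medication rules apply as follows: "If the partial start date does not indicate whether the medication started prior to or after double-blind treatment", and "If the partial end date does not indicate that the medication ended prior to the start of double-blind treatment". In either case the drug is classed as both prior and concomitant.

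**Design and anchors elsewhere.** On blinding, Protocol 4.5 says "Not applicable. This is an open-label study". SAP 2.2 agrees: "This is a multicenter, open-label study designed to assess long-term safety and tolerability of CBD in patients with PWS". SAP 6.7.2 defines TEAEs as events with "start date on or after the date of first dose of IMP and up to 14 days after the last dose of IMP", and adds pre-dose events that worsen after first dose in INS011-17-115. SAP 6.4.2 separates prior from concomitant medications at the first IMP dose in INS011-16-085.

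**The concern.** Incidence, type and severity of TEAEs is the first safety endpoint in SAP 3.1, and safety is the trial's only objective. Once a missing grade has been set to severe, the SAP gives no reason to drop the event from the table that names its type. The overview table could then report a patient with a severe TEAE who appears in no SOC or PT row, and the affected term would be understated.

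The date rules raise a smaller issue. They name a treatment period that does not exist in this trial, and SAP 6.7.2 and 6.4.2 need two different dates where SAP 5.2 supplies one phrase. Some AEs with an uncertain onset near first dose also receive no class, so someone would have to decide them outside the plan.

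**Working it through.** The documents give no calculated figure on this point, so there is none to reproduce. The check sets the rules side by side and applies them literally.

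**1. Missing severity: one event, two treatments.**

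| Patient's TEAEs in a PT | Overview table | Maximum-severity SOC/PT table |
|---|---|---|
| One event, severity missing | Any TEAE: yes; severe: yes | Not counted |
| One mild event and one with severity missing | Any TEAE: yes; severe: yes | Counted as mild, since the missing one is excluded |

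The patient disappears from a term only when all of that patient's events in the term lack severity.

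**2. Number of summaries reached.** SAP 6.7.2 lists 10 SOC/PT summaries:

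- all TEAEs, related TEAEs, and TEAEs by relationship (3)
- by maximum severity, and related by maximum severity (2)
- causing discontinuation, and related causing discontinuation (2)
- serious, and related serious (2)
- leading to death (1)

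The total is 3 + 2 + 2 + 2 + 1 = 10. If the exclusion belongs only to the maximum-severity sentence before it, 2 of 10 are affected. If it belongs to the whole paragraph, up to 10 of 10 are affected.

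**3. Size per term.** The maximum n is 66 (SAP 2.3). The loss is k/66 for k patients whose only events in the term lack severity. The documents do not give k, so 0 to 3 is an assumption:

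- k = 0: 0 points
- k = 1: 1/66 = 1.5 percentage points
- k = 2: 2/66 = 3.0 points
- k = 3: 3/66 = 4.5 points

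Within a modal-dose group smaller than 66, each patient weighs more.

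**4. Anchors for the date rules.** All four rules (2 AE + 2 medication) use the double-blind term.

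| Rules | Definition they serve | Anchor in that definition |
|---|---|---|
| 2 AE rules | SAP 6.7.2 | First and last IMP dose, with the worsening clause naming INS011-17-115 |
| 2 medication rules | SAP 6.4.2 | First IMP dose in INS011-16-085 |

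The 14 days in AE rule 1 match the 14 days in SAP 6.7.2, so the AE meaning can be recovered. The medication anchor is a different date.

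**5. AE rules with the SAP 6.7.2 anchor put in.** Take five onset states: missing; partial and unclear against first dose only, the window's end only, or both; and partial but clearly inside the window. Take five end-date states: complete before first dose; complete on or after it; partial and clearly before; partial and not clearly before; and absent or ongoing. That gives 5 × 5 = 25 combinations. Four are impossible (onset not before first dose, end before it), leaving 21.

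- In 8 of the 21, no written rule gives a class. Four of these ended before first dose and are non-emergent by inference.
- The other 4 have no answer: onset missing, or unclear only against first dose, paired with an end date that is complete on or after first dose, or with an ongoing event.
- In 2 further combinations (onset unclear against both limits, event known to have ended before first dose), rule 1 read literally makes the event treatment-emergent.

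These are counts of logical cases, not of expected events.

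**The case against.** **Scope of the severity exclusion.** It directly follows the sentence on maximum-severity tables and may have been meant only for them. The main TEAE table by SOC and PT would then be untouched. This stands as a limit: a reader might infer that all 10 summaries are understated, but the text does not settle that. It does not remove the contradiction, because the two maximum-severity tables are affected on either reading.

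**The double-blind wording is carry-over text.** For AEs this is fair, since SAP 6.7.2 supplies the meaning. For medications, the phrase might point to INS011-16-085, in which case those two rules may already agree with SAP 6.4.2. The documents do not state that study's design. Even so, that reading would set the AE rules against SAP 6.7.2, so one phrase cannot serve both.

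**The gap at first dose is narrow.** A reader might infer that most AEs with incomplete dates go unclassified. The documents do not support this: 4 of 21 combinations lack an answer. For a patient who stops very early, a month-only onset can also be unclear against the window's end, and rule 1 then classes it. Protocol 6.1.7.1 sends AEs reported before dosing to medical history. Events listed in SAP 6.7.2 as ongoing from INS011-16-085 are already known to have begun there, so their class turns on worsening, not on a partial onset date. What remains is mostly missing detail.

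**Medication end dates.** A reader might infer that SAP 5.2 labels as prior a drug with a partial end date and a known start after the anchor dose. That is over-literal. SAP 6.4.2 already makes such a drug concomitant, and the partial-date rule is needed only when the dates leave the class open.

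**Safeguards.** Investigators must rate intensity, and SAE reports must carry the onset date (Protocol 6.1.7.7). Sites must resolve data queries (12.1), and the sponsor reviews all CRF data before lock (10.3). These make missing values less likely and support a minor rating.

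**Conclusion.** SAP 6.7.2 contradicts itself on missing severity. Followed as written, it can understate a term in at least 2 and at most 10 of the 10 SOC/PT summaries, by 1.5 percentage points per lost patient at n = 66. The size rests on an unknown number of missing grades, which may be zero.

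The double-blind anchor in all four SAP 5.2 rules is a genuine error in an open-label trial, but secondary: the AE and medication anchors can be taken from SAP 6.7.2 and 6.4.2. The unclassified onsets near first dose should be settled in the same edit.

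The whole point is minor. Protocol 8.5.3 plans no inferential safety analysis, SAP 6.7.2 rules out comparisons of AEs between groups, and the listings keep every event.

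**What to change.** 1. **SAP 6.7.2:** delete the exclusion, so that TEAEs with missing severity count in every SOC/PT summary, and as severe wherever severity is tabulated.
2. **SAP 5.2, anchors:** replace the double-blind term with first and last IMP dose in INS011-17-115 in the two AE rules, and with first IMP dose in INS011-16-085 in the two medication rules.
3. **SAP 5.2, AE rule:** class an AE with partial or missing onset as treatment-emergent, including when the end date is complete on or after first dose or the event is ongoing, unless the available dates show onset more than 14 days after last dose, onset before first dose, or end before first dose.
4. **Carried-over events:** state that an event recorded as ongoing from INS011-16-085 is treatment-emergent only if its recorded severity worsens on or after first dose in INS011-17-115. Without this, such an event with no onset or end date would become treatment-emergent by default. Dates alone cannot show whether it worsened.

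The cost is one deletion in SAP 6.7.2 and a few sentences in SAP 5.2. No new data are needed.

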6.1 General Principles

All data processing, summarization and analyses will be performed using Covance's SAS Environment / Version 9.4 (or later) of the SAS® statistical software package.

The analysis treatment group will be defined by the modal dose of study drug (dose of the study drug that the patient took for the longest period).

The following principles will be applied to all TFLs unless otherwise stated:

Principle	Value		
Significant tests	Two-sided and use a 5% significance level		
Treatment group labels	Listings:		
and order presented	Cannabidiol Oral Solution (20mg/kg/day)		
	Cannabidiol Oral Solution (30 mg/kg/day)		
	Cannabidiol Oral Solution (40 mg/kg/day)		
	Tables:		
	CBD (20 mg/kg/day)		
	CBD (30 mg/kg/day)		
	CBD (40 mg/kg/day)		
	All CBD		
Tables	Data in summary tables presented by treatment group and visit (where applicable)		
Listings	All data collected presented by		
	Treatment group		
	Patient		
	Visit (where applicable)		
	Date;		
	unless otherwise specified		
Descriptive summary	Number of patients/observations (n)		
statistics for continuous variables	Mean		
	Standard deviation (SD)		

Sponsor Name: Insys Development Company, Inc.

Sponsor Protocol ID: INS011-17-115 Covance Study ID: 000000163385

Principle	Value
	Median
	Minimum
	Maximum
Descriptive summary statistics for categorical variables	Frequency counts and percentages [n (%)]
Denominator for percentages	Number of patients in the analysis population, unless stated otherwise in table shell(s)
Include "Missing" as	Yes, when the number missing is greater than zero for at
category	least one treatment group
Display for 0	Leave blank
percentages	
Display to one more decimal place than collected value	Mean Mean Difference
	Median Percentages
Display to two more	Standard Deviation
decimal places than collected value	Confidence Interval
Limit of precision for displays	3 decimal places

Baseline is defined as Visit 10 of INS011-16-085.

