3.4. Dose Adjustment Criteria

Patients may have their dose of study medication adjusted down once from 40 mg/kg/day to 30 mg/kg/day or 30 mg/kg/day to 20 mg/kg/day at the discretion of the Investigator or qualified designee based on the patient's tolerability. If the lower dose is not tolerated, the drug will be discontinued and the patient will be withdrawn from the study.

All dose changes must be clearly documented in the eCRF.

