- Study drug discontinued
- Dose modified
- Required concomitant medication
- Required procedure
- Other

6.1.7.6. **Outcome at the Time of Last Observation**

The outcome at the time of last observation will be classified as:

- Recovered/resolved
- Recovered/resolved with sequelae
- Not recovered/not resolved
- Death
- Unknown

6.1.7.7. **Adverse Event Recording and Reporting**

Adverse events will be recorded throughout the study in the source documents and in the CRFs. The investigator will rate AEs for seriousness, intensity, causality, action taken, and outcome as described in the previous section.

Expedited reporting is required for serious unexpected adverse drug reactions. Fatal or life-threatening unexpected drug reactions must be reported by the Sponsor to regulatory agencies no more than 7 days after the Sponsor's first knowledge of the reaction; followed by as complete a report as possible within 8 additional days. Unexpected drug reactions must be

reported no later than 15 days after the Sponsor's first knowledge of the reaction. In order to comply with these requirements, the investigator or delegate must inform the Sponsor immediately upon occurrence of any SAE. The site will complete the SAE Report Form as thoroughly as possible and e-mail it to Insys within 24 hours of the investigators first knowledge of the event.

Sponsor contact information is listed below:

Insys Development Company, Inc.

Email: [contact]

These SAE reports must contain the following information:

- A. Study name/number
- B. Study drug
- C. Investigator details (name, phone, fax, e-mail)
- D. Patient number
- E. Patient initials
- F. Patient demographics
- G. Clinical event
 - 1) Description
 - 2) Date of onset
 - 3) Treatment (drug, dose, dosage form)
 - 4) Adverse event relationship to study drug
 - 5) Action taken regarding study drug in direct relationship to the AE
- H. If the AE was fatal or life-threatening
- I. Cause of death (whether or not the death was related to study drug)
- J. Autopsy findings (if available)

The Sponsor or its representative will be responsible for notification to regulatory agencies.

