8.5.1. Study Patients and Demographics

8.5.1.1. Disposition and Withdrawals

The numbers of patients entering, completing, and withdrawing, along with reasons for withdrawal, will be tabulated overall and by modal dose group. For each patient, the modal dose is the dose with the longest exposure during the study.

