8.5.3.1. Adverse Events

The Medical Dictionary for Regulatory Activities (MedDRA, version 20.0 or higher) will be used to classify all AEs. Adverse event summaries will include only TEAEs, which will be summarized for each modal dose group. For each patient, the modal dose is the dose with the longest exposure during the study.

The number and percentage of patients with AEs will be displayed for each treatment group by system organ class and preferred term. Summaries of AEs by severity and relationship to the IP will also be provided. Serious AEs (SAEs) and AEs resulting in discontinuation will be summarized separately in a similar manner. Patient listings of AEs and SAEs will be produced.

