6.7 Safety

6.7.1 Extent of Exposure

Duration of exposure will be defined in days as:

(date of last dose - date of first dose) + 1.

Duration of exposure will be summarized using descriptive statistics for each treatment group for the enrolled population.

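### TEAE tables use only the dose taken longest, so after a tolerability step-down events can be counted under a dose the patient was not taking

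*SAP*

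**What the plan says.** **Grouping.** SAP 6.1: "The analysis treatment group will be defined by the modal dose of study drug", meaning the dose taken for the longest period. This governs all tables, figures and listings unless otherwise stated, and SAP 6.7.2 does not state otherwise. Protocol 8.5.3.1: "Adverse event summaries will include only TEAEs, which will be summarized for each modal dose group". Protocol 8.5.1.1 defines the term: "For each patient, the modal dose is the dose with the longest exposure during the study". The table columns in SAP 6.1 are labelled by dose alone, for example CBD (40 mg/kg/day), plus All CBD.

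**Dose changes.** Protocol 3.4: "Patients may have their dose of study medication adjusted down once from 40 mg/kg/day to 30 mg/kg/day or 30 mg/kg/day to 20 mg/kg/day", on grounds of tolerability. SAP 2.2 repeats this ("or from 30 mg/kg/day to 20 mg/kg/day at the discretion of the Investigator or qualified designee"). Protocol 1.5 and 4.3 speak more generally of adjustment at the investigator's discretion, with 40 mg/kg/day as the ceiling.

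**Data collected.** Protocol 3.4: "All dose changes must be clearly documented in the eCRF". The actions that can be recorded for an adverse event (protocol 6.1.7.5) include "Dose modified".

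**Summaries described.** SAP 6.7.2 lists TEAE tables by relationship, severity, seriousness, discontinuation and death. On exposure, SAP 6.7.1 says: "Duration of exposure will be summarized using descriptive statistics for each treatment group for the enrolled population". That duration runs from first to last dose, whatever the dose level. The SAP text describes no summary by dose at onset, of time on each dose, or of TEAEs leading to dose reduction.

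**The concern.** The grouping variable is fixed only after treatment has run its course, and the outcome being tabulated can alter it. A patient who starts on 40 mg/kg/day, has an adverse event, steps down early and then does well on 30 mg/kg/day appears, with that event, in the 30 column. The patient also leaves the denominator of the 40 column. The reverse also happens: a patient who steps down late stays in the 40 column, and any later event at 30 is counted there.

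The trial's only objective is long-term safety and tolerability. Dose reduction is itself a tolerability outcome, yet the SAP text does not tabulate it. Because the columns carry a plain dose label, a reader will naturally take them as event rates on that dose, which after a step-down they are not.

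**Working it through.** **1. Break-point.** Let T be the days of exposure and t the days at the higher dose before a single step-down. The higher dose has t days and the lower dose T − t, so the lower dose is modal when t < T/2.

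- T = 48 × 7 = 336 days: the lower dose is modal for t up to 167, day 168 is an exact tie, and the higher dose is modal after that. The switch is at week 24.
- Safety Period of 48 ± 2 weeks: T = 322 gives a tie at day 161 (week 23), and T = 350 a tie at day 175 (week 25).
- Early withdrawal: half of actual exposure, for example week 12 of 24.
- Three taper days at 20 mg/kg/day, after a step from 40 to 30, do not move the switch.

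For a completer, a step-down at the week 4, 8 or 12 visit puts the patient in the lower-dose column, and one at week 36 leaves the patient in the higher. Week 24 (Visit 5) is the tie, and neither document gives a tie rule.

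**2. Illustrative size for any TEAE in the 40 mg/kg/day column.** The documents give no starting-dose split and no number or timing of reductions for this study, so every input here is an assumption:

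- c = 22 start on 40 (66/3);
- r = 10, 4 or 2 of them reduce;
- e = r/2 reduce early;
- every reducer has a TEAE while on 40;
- a share p of non-reducers has a TEAE;
- nobody moves up to 40.

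The upper value r = 10 borrows the 9/20 reductions at 40 mg/kg/day that protocol 1.3.3 reports from the sponsor's 48-week epilepsy extension (0.45 × 22 = 9.9). That is a different population, and the protocol does not say who the 20 were. 20/52 = 38% also matches the share that protocol 1.3 describes as tolerating 40, so they may not be starters. Hence the cases with 4 and 2. For p, 69% is the placebo any-AE rate in the 14-week Lennox–Gastaut trial in protocol 1.3.3, again a different population, and 30% is simply a lower value.

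Formulas:

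- Among starters on 40: (r + (c − r)p)/c
- Modal-40 column: (r − e + (c − r)p)/(c − e)
- Shortfall: (1 − p)(c − r)e / (c(c − e))

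| r, e | p | Starters on 40 | Modal-40 column | Shortfall (points) |
|---|---|---|---|---|
| 10, 5 | 0.30 | 13.6/22 = 61.8% | 8.6/17 = 50.6% | 11.2 |
| 10, 5 | 0.69 | 18.28/22 = 83.1% | 13.28/17 = 78.1% | 5.0 |
| 4, 2 | 0.30 | 9.4/22 = 42.7% | 7.4/20 = 37.0% | 5.7 |
| 4, 2 | 0.69 | 16.42/22 = 74.6% | 14.42/20 = 72.1% | 2.5 |
| 2, 1 | 0.30 | 8/22 = 36.4% | 7/21 = 33.3% | 3.0 |
| 2, 1 | 0.69 | 15.8/22 = 71.8% | 14.8/21 = 70.5% | 1.3 |

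**3. Why the direction is not settled.** The table can show only a shortfall, because every reducer is assumed to have an event on 40. A single preferred-term row can go either way. Take r = 10 and e = 5, and suppose 4 reducers have a given term while on 40, 2 of them early reducers. The rate on 40 is 4/22 = 18%, and the column shows 2/17 = 12%. Now suppose 2 of the other late reducers have the same term only after stepping down. The rate on 40 is still 4/22 = 18%, but the column shows 4/17 = 24%.

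**The case against.** Modal dose is a recognised descriptive convention, fixed in advance and defined consistently in both documents. It places each patient in exactly one column. The objective concerns CBD overall, not dose-response. SAP 6.7.2 rules out statistical comparison of AEs between groups, no randomisation to dose is described, and All CBD is unaffected. AEs are listed and dosing is listed in full (SAP 6.5), so dose at onset can be worked out for at most 66 patients. TEAEs leading to discontinuation are tabulated. Early reductions may be few, because patients have completed the feeder study and exclusion criterion 4 can keep out those with a CBD-related event.

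All of this stands, and it limits the point. It does not remove it: tracing across listings is not a summary, and three adjacent columns labelled by dose will be read as rates by dose even without a test.

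Two stronger readings are tempting. One is that the tables systematically understate events at the higher dose and overstate them at the lower. Section 3 of the working shows why that does not follow. The other is that no relevant table will be produced. SAP 6.1 refers to table shells that are not among the documents, so only the silence of the SAP text can be shown.

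**Conclusion.** The point holds as a limitation of the planned display. For any patient who steps down, the dose column reflects the longer of two exposures and not the dose at the time of the event. The switch falls at about week 24 for a completer and at half of actual exposure for an early withdrawal. Misattribution runs both ways, and the documents do not allow its net direction or size to be determined.

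Under the assumptions above, with 2 to 10 of 22 starters reducing and background rates of 30% to 69%, the any-TEAE figure in the 40 mg/kg/day column is about 1 to 11 points low. A reader might infer a gap as large as 16 points by setting the background to zero with 10 reducers (12 × 5/(22 × 17) = 16.0%). That requires no TEAE in any non-reducer over 48 weeks, which nothing in the documents supports. Nor do they support a figure for the 30 mg/kg/day column: the remaining patients of the epilepsy extension were not a 30 mg/kg/day group, since doses there ranged from 10 to 40.

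The study is not invalidated. This is a cheap improvement, best made before database lock.

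**What to change.** - **SAP 6.1:** keep the modal-dose tables, label their columns 'modal dose', and add a one-line tie rule.
- **SAP 6.7.2 and protocol 8.5.3.1:** add descriptive TEAE summaries by the dose being taken at onset, or at worsening for events that began before the first dose. Use patients exposed and patient-years at that dose as denominators.
- **SAP 6.7.2:** add a table of TEAEs with the action "Dose modified", by dose at onset. The recorded action has no direction, so take the direction from the dosing records.
- **SAP 6.7.1:** add time on each dose.
- **Direction of dose changes:** reconcile protocol 1.5 and 4.3, which can be read either as a cap or as allowing upward adjustment, with protocol 3.4 and SAP 2.2, which describe only a step-down. Upward changes would also alter modal assignment.

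**Cost.** A few tables from data already collected, plus short conventions for partial onset dates that span a dose change and for events in the taper or within 14 days after the last dose. SAP 5.2 settles only whether such events are treatment-emergent.

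**Downsides.** A patient can appear in more than one dose column, so the columns will not sum to All CBD. Lower-dose columns will include later time from patients who stepped down, which confounds dose with time on drug and with tolerability. Footnote the new tables as descriptive and not a dose comparison.
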